## **8.0 Data Collection and Management Procedures**

### Aim 1: Formative Research

**Scenario-Based Evaluations** by the 2 independent PST master trainers are completed and stored on REDCap at UIC.

**Formative User Study** data from audiorecorded Zoom conference session, with participant’s explicit permission.

## Aim 2: Pilot RCT

The study coordinators are trained on data collection according to standardized protocols, and their performance is continuously monitored. The following types of data are collected.

1. Data on diagnoses, prescriptions, clinical encounters, and hospitalizations are abstracted from EHR for eligibility screening and baseline characterization.
2. fMRI data and physical measurements are collected at the UIMC Advanced Imaging Center.
3. Survey data and ecological daily assessments are collected using self- and interviewer-administered questionnaires on REDCap, a HIPAA-compliant server.
4. With participant's explicit permission, PST sessions are audiorecorded and are stored in study configured accounts on the AWS cloud, accessible only by study staff.

See Appendix 2 for the list of study measures and assessment schedule.

### **8.1 Data Management**

**Neuroimaging data management.** There are Linux machines dedicated to various aspects of image transfer and storage available to the MPI [name] and team within the UIC Psychiatric Institutes. The Institute also houses an imaging processing server for data storage and analysis (Dell PowerEdge R900, 2.13 GHz, Xenon Four Cores, 128GB RAM with 6 TB of data storage). These machines are networked with a T3 line to facilitate image transfer and back-up of data from the Center for MR Research. The T3 line is connected to the University network and firewall shielded from the outside. These machines are for the sole use of the research team and as such the research team has its own log in for the system with direct access from our dedicated research computers.

**Non-imaging data management.** REDCap study database on a HIPAA-compliant server, occur automatically according to a preset schedule (no participant action required). Data are immediately available for inspection and reporting of recruitment and retention status and any missing data. The data analyst performs weekly quality controls.

All datasets are cleaned, verified, and archived. One official copy of all study data and a master data dictionary are maintained and updated regularly. All analytic and tracking databases are stored on a HIPAA-compliant server with continuous backups. For the protection of participant confidentiality, unique anonymous study IDs are used for data storing, tracking, and reporting. PHI is stored separately from all other study data and will be used and disclosed in accordance with the HIPAA regulations. Regular reports are produced on (1) patient accrual and follow-up completion/retention in relation to goals and timeline; (2) the randomization process and group comparability on the balancing variables; (3) key baseline characteristics of the sample, by (blinded) group, related to the primary and secondary outcome variables; (4) intervention exposure and adherence; and (5) protocol violations. Any observed delays in these processes or data irregularities shall be followed up and resolved in a timely manner.

**Data sharing.** De-identified fMRI data and other study data are shared with collaborators at UIC and other collaborating institutions via a UIC Box Health Data Folder. All collaborating institutions are listed as data users under the HIPAA regulations and authorization provided by participants. PHI (e.g., name, address, phone number) and the link between study ID and the patients' identities will not be shared. They can download data from the UIC Box Health Data Folder and store them on a HIPAA-compliant server at their institution for analysis according to the study protocol. We follow the latest industry standards for data encryption, server authentication, and client authentication to ensure secure data transmissions at all times. In addition, all the investigators and staff maintain up-to-date trainings and certifications in human subject's protection, HIPAA, and Good Clinical Practice (GCP). Furthermore, we will partner with the NIMH and use all NIMH data preparation and sharing policies as a guide to ensure the deidentified data and results, along with all associated documentation, are submitted to the NIMH

Data Archive (NDA), to be specifically deposited to the National Database for Clinical Trials Related to Mental Illness (NDCT). We will ensure we have permission from our participants to disclose deidentified participant-level data collected as part of this study to researchers who meet all the NDCT requirements for requesting use of the dataset. We will strictly comply with the HIPAA and IRB regulation requirements regarding research use of PHI and appropriate safeguards for sharing deidentified data.

## 9.0 Data Analysis and Statistical Considerations

### Aim 1: Formative Research

**Formative User Study.** We will conduct the following analyses: (1) analysis of verbal interactions with Lumen to measure interaction efficiency, including breakdowns in conversations (e.g., stoppages) and pauses that break the flow and continuity, and consequently, the efficiency of the conversational interaction; (2) analysis of Digital Health Literacy Instrument, task load (NASA Task Load Index (NASA-TLX) of user workload along with 6 dimensions of mental, physical, temporal, performance, effort and frustration), user experience (User Experience Questionnaire-Short version (UEQ-S),) and therapeutic alliance (Working Alliance Inventory adapted for digital interventions (WAI-Tech) and (3) content analysis of audiorecordings of the walkthrough sessions. Quantitative survey data are summarized with descriptive statistics using SAS software (version 9.4; SAS Institute Inc.). Qualitative data are analyzed using the content analysis method described above.

### Aim 2: Pilot RCT

Pilot RCT sample size calculation using a confidence interval approach: To obtain a precision interval with a standardized half-width of 0.50 (akin to a medium effect) with 90% assurance, we have planned a sample size of 60 ( $n_{Trt}=40$ ,  $n_{Con}=20$ ), assuming  $\geq 85\%$  retention at 16 weeks. This provides reliable estimates of between-treatment differences in change in amygdala activation for nonconscious threat-related reactivity and change in DLPFC activation for cognitive control from week 0 to 16 in Criterion 1. In Criterion 2, a sample size of 60 will also be sufficient to detect a correlation coefficient of  $r=0.4$  with 0.80 power and 2-sided  $\alpha=0.05$ . We are not focused on smaller correlations ( $r<0.4$ ) because their implications are likely to have more limited clinical relevance.

The criteria to evaluate neural target engagement are as follows:

**Criterion 1.** The level of task-evoked activation for either the amygdala for nonconscious threat-related emotional reactivity or for the DLPFC for cognitive control improves meaningfully from week 0 to 16 in the Lumen group compared with the waitlist control group.

Criterion 1 is tested via  $t$  test that compares the change from week 0 to 16 in the Lumen group with that change in the waitlist control group. Participants are analyzed based on the group to which they are assigned using all available data. The  $t$  test described above can be readily expanded for exploratory subgroup analyses by applying to each subgroup (e.g., female vs. male).

**Criterion 2.** Change in the level of task-evoked activation of a neural target that meets Criterion 1 correlates with temporally concurrent change from week 0 to 16 in self-reported measures within the corresponding PST theory-based construct for emotional reactivity or cognitive control. We consider correlations of  $r\geq 0.4$  meaningful.

To test Criterion 2, we examine the regression change of the amygdala activity from week 0 to 16 on change in self-reported measures of emotional reactivity (worry, affect) from week 0 to 16, controlling for baseline values of the self-reported measures and group assignment. We expect that the coefficient for the change in amygdala activation is significant and positive in the direction of improvement in its

corresponding, validated emotional reactivity self-report measures and that this relationship may be significantly modified by group assignment. Similarly, we examine the regression change of the DLPFC activity from week 0 to 16 on change in self-reported measures of cognitive control (problem solving, dysfunctional attitudes) from week 0 to 16, controlling for baseline values of the self-reported measures and group assignment. We expect that the coefficient for the change in DLPFC activation is significant and positive in the direction of improvement in its corresponding, cognitive control validated self-report measures and that this relationship may be significantly modified by group assignment.

In addition, we will also conduct exploratory and secondary analyses. We will conduct an exploratory whole-brain analysis (1) to verify our *a priori* specification of neural targets, namely, amygdala for emotional reactivity and DLPFC for cognitive control, and (2) to identify any additional voxel clusters that are activated by our tasks and are associated with treatment response. Secondary analyses compare differences in discrete changes in PROs from week 0 to 16 and trajectories of change based on intensive time-series ecological measures between the Lumen and waitlist control groups. Analyses of the treatment effects on PROs employ the same *t* test approach as described above for testing Criterion 1 for target engagement. Furthermore, dosing analyses are conducted within the Lumen treatment group. The primary dosing analysis examines the relationship of neural target activation in the amygdala and DLPFC to the 4 measures of dose (number and length of PST sessions, fidelity-weighted number, and length of PST sessions). The secondary dosing analysis examines the relationship of patient-report outcomes, ecological end-of-day assessments, and measures of treatment progress (e.g., PHQ9 and GAD7 across PST sessions) to the same 4 measures of dose. Given neural target activation measures and PROs are obtained at weeks 0 and 16, these analyses focus on change over the full 16-week span of the study, whereas ecological end-of-day assessments and treatment progress measures are available for a total of 8 occasions each, and thus will be considered longitudinally.

Please see Appendix 3 for detailed power analysis and statistical analysis plan.

## 10.0 Quality Control and Quality Assurance

REDCap built-in quality control features (e.g., data type validation, valid values/range rules, required responses) and extensive data rules are used to allow for complex real-time quality control (QC) checks (e.g., of missing values, out of range values, logic comparisons, cross form/event consistency). When issues are identified through weekly and monthly scheduled QC checks, the data analyst will use the “REDCap data resolution workflow” feature, a built-in data query tool, to communicate the issues to study coordinators for resolution. Study coordinators can add notes or corrections within the data query tool and have editing rights to alter the source data, but all edits must be approved by the project manager. REDCap tracks all correspondence and decisions of the query process, and it maintains an extensive audit trail of access, entry, and edits of stored data. REDCap also allows for form and record locking capability with e-signature management.

## 11.0 Data and Safety Monitoring

The following Data and Safety Monitoring Plan (DSMP) will be followed to ensure the safety of study participants and the validity and integrity of data in compliance with NIMH requirements.

**Independent Oversight.** Because the risks for adverse events (AEs) and data breaches are minimal in the pilot RCT, and the study is not a Phase III clinical trial, it is determined that a Data and Safety Monitoring Board (DSMB) is not needed. Instead a safety monitor *independent of* the study is responsible for overseeing the implementation of this DSMP to ensure (1) the protection and safety of human subjects and (2) the validity and integrity of the trial. [name], MD, o at the University of Illinois at Chicago (UIC), serves in this role. The safety officer is responsible for examining aggregate data on

recruitment and retention, adverse events (unexpected or serious), and subject complaints, but he will not be reviewing individual, identifiable, subject data. If unexpected or serious adverse events occur, these will be reported to the IRB in the form of Prompt Reports. See further details below.

Contact PI [name] and senior biostatistician [name], both of whom will be blinded during the pilot RCT, meet with [name] every 6 months during active participant recruitment and follow-up to present and discuss data and safety monitoring information (below). For the annual continuing renewal application to the IRB and the annual progress report to the sponsor each year, [name] will provide a summary of her findings and recommendations regarding the following:

- ascertainment and any actions to be taken in response to AEs and SAEs reported during the study
- reports related to study operations and the quality of the data
- possible modifications in the study protocol concerning recruitment, participant retention, data quality, or trial operations more generally.

**Safety Monitoring.** As in any clinical trial, it is not possible to anticipate all possible AEs. Staff will undergo extensive training in ascertaining, monitoring, and documenting AEs—serious or not. The study investigators have extensive experience in clinical trial organization and management, including data and safety monitoring for single site and multisite trials. Established procedures for rendering first aid and life-threatening emergencies will be monitored by [name] (psychiatrist).

An AE is defined as any untoward medical or psychological event experienced by a patient during or as a result of his/her participation in the study that represents a new symptom or an exacerbation of an existing condition whether or not considered study-related based on appropriate medical judgment. SAEs are any adverse experience that results in any of the following outcomes:

- Death
- Life-threatening event/illness
- Inpatient hospitalization or prolongation of existing hospitalization
- Persistent or significant disability/incapacity
- Pregnancy resulting in a congenital anomaly/birth defect
- Any event requiring medical or surgical intervention to prevent permanent impairment or damage. In this study, this is defined as physician confirmed diagnosis of any of the following: angina pectoris, heart attack, stroke, transient ischemic attack, heart failure, coronary angioplasty or bypass surgery, peripheral vascular disease, , any other serious injury to the bone or muscle, liver failure, kidney failure, and cancer (except for non-melanoma skin cancer).

Non-serious AEs are all adverse events that do not meet the above criteria for “serious.” To ensure unbiased ascertainment, AEs will be systematically identified by querying participants at 16-week follow-up visits using the AE Patient Query Form. In order to access the electronic medical record, as needed, for AE adjudication, consenting participants are asked to provide and/or confirm the minimum necessary identifiers including first and last name, date of birth, mailing address, and whether they have received care at UI Health.

**Blinded Reporting.** In the pilot RCT, safety information will be monitored while keeping the true identity of the study groups masked. In his role as the study physician, [name] may need to become unblinded. But Contact PI [name] and biostatistician [name] as well as the independent safety monitor [name] will be blinded throughout the study and will review summaries of the numbers and rates of all AEs by blinded treatment group. Proper blinding of the other investigators and outcome assessors will be enforced as well.

**Requirements for Adverse Event reporting.** The Contact PI, [name], will inform the Director of IRB panel and all relevant oversight committees at the university within 5 business days of learning of an unanticipated AE or major protocol deviation. All relevant information will be reported to the IRB for each unexpected SAE including information about the event and its outcome, dosing history of a suspect medication/treatment, concomitant medications, the participant's medical history and current conditions, and all relevant laboratory data. Within 15 business days of the PIs becoming aware of changes in risk/benefit or events requiring report to the sponsor, these will be reported. This timeline satisfies the NIMH reporting requirements for AEs and unanticipated problems. An annual report will be submitted to the IRB and to the sponsor summarizing all AEs, serious or not.

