approved ENGAGE-2 study #2018-1174), is in place to immediately alert the study supervising psychiatrist to assess the patient’s suicidal thoughts by telephone, followed by notification of the participant’s PCP and appropriate clinical action if necessary. If a participant responds “1” (“several days”), “2” (“more than half the days”), or “3” (“nearly every day”) to the PHQ-9 question “Over the last 2 weeks, how often have you been bothered by thoughts that you would be better off dead or thoughts of hurting yourself in some way?”, we further assess the participant’s level of risk by asking “Do you have a plan for how you would commit suicide?” and then follow the protocol based on the assessed level of risk. Individuals reporting suicidal ideation on PHQ9 with an active plan at eligibility screening are excluded from participation. Nonetheless, the risk of emergent suicidality still exists after enrollment. Risk for suicide may be detected when a participant completes the PHQ9 at the beginning of each PST session with Lumen. Participants who score 1-3 (see above) on item 9 of the PHQ9, will be offered the option to call an emergency contact, the national [name]/[name] hotline, or 911 at the time of detection. This information is a pre-programmed script for Lumen. The supervising study psychiatrist, [name], the intervention manager, [name], receive immediate notifications, as outlined in the table below. The study psychiatrist calls the participant within 3-4 days to conduct an assessment, assess need for further referral, and discuss referral options depending on urgency, needs and preferences, available supports in place, insurance status and routine source of care. The study psychiatrist may refer the participant for immediate comprehensive evaluation (e.g., at a local emergency department), ambulatory psychiatric services, or community resources, with personal accompaniment depending on the evaluation outcome.

[If PHQ9 completed with SPEAC study staff by phone]	

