### Aim 2: Pilot RCT

The study uses a 2-step consent process, an online screening consent is first obtained prior to initial eligibility screening, which facilitates participant self-screening. Second, screened eligible and interested participants are invited to attend a teleorientation with study staff who lead a full informed consent discussion and use the eConsent framework to provide written informed consent documentation (ICD).

All participants document their consent electronically using the secure REDCap eConsent framework and obtain their pdf copy of the signed consent by directly downloading through REDCap. The study copy is

automatically archived in the file repository in REDCap database, which is a HIPAA-compliant server, accessible to the PIs and study personnel.

**Subject Confidentiality.** See Protection against breaches of participant privacy and confidentiality in Section 7.0.

**Unanticipated Problems.** An unanticipated problem (UP) is defined to include any incident, experience, or outcome that meets all of the following criteria:

- \* Unexpected (in terms of nature, severity, or frequency) given (a) the research procedures that are described in the protocol-related documents, such as the IRB-approved research protocol and informed consent document; and (b) the expected natural progression of any underlying disease, disorder, or condition of the subject experiencing the UP and the subject's predisposing risk factor profile for the UP;
- \* At least possibly related to participation in the research (possibly related means there is a reasonable possibility that the incident, experience, or outcome may have been caused by the procedures involved in the research); and
- \* Suggests that the research places subjects or others at a greater risk of harm (including physical, psychological, economic, or social harm) than was previously known or recognized.

Within 5 business days of the PI learning of a UP or major protocol deviation, the PI informs the Director of IRB panel and all relevant oversight committees at the university. Within 15 business days of the PI becoming aware of non-serious AE, changes in risk/benefit, or events requiring report to the sponsor, these will be reported. An annual report will be submitted to the IRB and the sponsor summarizing all AEs, serious or not.

[figure not shown]

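### The intervention criterion for a serious adverse event is closed to a list of somatic diagnoses that omits self-harm, and the reporting paragraphs disagree on serious but expected events

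*Combined protocol and SAP*

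**What the plan says.** **Classification.** Section 11.0 (Safety Monitoring) counts both medical and psychological events as adverse events. It opens the serious category with "SAEs are any adverse experience that results in any of the following outcomes" and gives six criteria: death, a life-threatening event, inpatient admission, lasting or significant disability, a congenital anomaly, and a sixth worded "Any event requiring medical or surgical intervention to prevent permanent impairment or damage". Only the sixth is qualified: "In this study, this is defined as physician confirmed diagnosis of any of the following: angina pectoris, heart attack, stroke". The list goes on through transient ischemic attack, heart failure, coronary procedures and peripheral vascular disease, has an empty place between two commas, and ends "any other serious injury to the bone or muscle, liver failure, kidney failure, and cancer (except for non-melanoma skin cancer". Whatever meets none of the six is non-serious.

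Section 7.0 puts self-harm first and MRI-related injury second among the study risks. After describing the exclusion of people with an active suicide plan, it adds: "Nonetheless, the risk of emergent suicidality still exists after enrollment".

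**Reporting.** Three paragraphs set the rules.
- Section 11.0, Independent Oversight: "If unexpected or serious adverse events occur, these will be reported to the IRB in the form of Prompt Reports".
- Section 11.0, Requirements for Adverse Event reporting: the IRB is told "within 5 business days of learning of an unanticipated AE or major protocol deviation", and full details are required for an unexpected SAE. Changes in risk/benefit and sponsor-reportable events have 15 business days. An annual report covers all events.
- Section 12.0, Unanticipated Problems: 5 business days for an unanticipated problem, which must be unexpected, at least possibly related and suggestive of greater risk. A further sentence begins "Within 15 business days of the PI becoming aware of non-serious AE, changes in risk/benefit, or events requiring report to the sponsor". The annual report is repeated.

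**The concern.** The sixth criterion, in its general wording, is the one that would most naturally catch an overdose or self-inflicted injury that is treated and discharged. The sentence after it replaces that wording with named diagnoses, and nothing marks them as examples. The result is an odd ordering for a trial in people with untreated depression or anxiety: a new outpatient diagnosis of peripheral vascular disease is serious, while some medically treated self-harm is not.

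The label carries weight here. There is no DSMB. A single independent safety monitor sees aggregate data, with meetings every 6 months, and the Independent Oversight paragraph describes the adverse events in that remit as unexpected or serious ones. The Blinded Reporting paragraph does add summaries of all adverse events by masked group. The pilot could still report no serious events although self-harm requiring medical intervention had occurred.

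The second issue is that site staff cannot tell from the three reporting paragraphs what to do with an event that is serious but judged expected, such as an admission for worsening depression.

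**Working it through.** No sample size, power or event rate bears on this, so the check is to set the rules side by side and route cases through them.

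**Legible entries in the sixth criterion:** angina; heart attack; stroke; transient ischemic attack; heart failure; coronary angioplasty or bypass; peripheral vascular disease; [blank]; other serious bone or muscle injury; liver failure; kidney failure; cancer. That is eleven legible entries and one blank. None of the eleven is psychiatric or names self-harm.

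**Case 1: self-harm treated without admission.** Assume treatment was needed to prevent permanent damage.
1. Adverse event: yes, psychological and medical events both count.
2. Death, admission, congenital anomaly: not met.
3. Life-threatening, or lasting or significant disability: these remain open. If either is met, the event is serious and the list does not matter.
4. If neither is met, only the sixth criterion is left. Its general wording is met. The study definition is not, unless the injury was a serious bone or muscle injury or produced a listed organ failure.
5. Result: non-serious, for that remaining group only.

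MRI-related injury follows the same route. The life-threatening, admission and disability criteria still apply to it; the gap is confined to the sixth.

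**Cases 2 to 4: reporting.** The documents do not define an unanticipated event in Section 11.0; the table reads it as unexpected.

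| Event | 11.0 Independent Oversight | 11.0 Requirements for AE reporting | 12.0 Unanticipated Problems |
|---|---|---|---|
| 2. Psychiatric admission, judged expected | Prompt Report, because serious | No 5-day clock, no detailed report; annual report | Not an unanticipated problem; not non-serious, so outside that 15-day class; annual report |
| 3. Non-serious, expected, unrelated | None | Annual report | 15 business days; annual report |
| 4. Non-serious, unexpected, unrelated | Prompt Report | 5 business days | Fails the relatedness test, so 15 business days |

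For case 2, Sections 11.0 and 12.0 both leave a 15-business-day route if the admission counts as a change in risk/benefit or as an event requiring report to the sponsor. The second class is not defined, and neither sentence says to whom the report goes.

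The table shows two discrepancies. A serious expected event is prompt in one paragraph and has no named clock of its own in the other two, while Section 12.0 gives a minor non-serious event 15 business days. Case 4 has 5 business days in one place and 15 in another.

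**The case against.** Several points on the other side are sound and limit the conclusion.

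- A reader might infer that a suicide attempt treated without admission is never serious. The text does not support that: the life-threatening and disability criteria are unrestricted and need no admission. Nor is MRI injury serious only when it affects bone or muscle. An emergency call for an active plan without injury is a weak example too, since it may not meet even the general wording of the sixth criterion.
- The blank place may be lost text, so an exact count of omitted items should not be pressed. The word *other* after the blank hints that the missing entry was an injury to bone or muscle, but that is inference. Whatever stood there, the list remains closed.
- A reader might infer that an expected admission waits up to a year for IRB notice. That is not established. The Independent Oversight paragraph points forward to further details, so the later paragraph can be read as supplying its clock rather than cancelling it, and the sponsor-reportable route may apply. On that reading, a Prompt Report and 5 business days in case 4 agree, and only the 15-day wording in Section 12.0 differs.
- Expected natural progression is a test in Section 12.0's definition of an unanticipated problem. It does not automatically govern the undefined terms in Section 11.0.
- Oversight exists outside the serious label: PHQ9 item 9 responses at PST sessions trigger immediate notification of the study psychiatrist, the monitor sees all adverse events by masked group, and the annual report covers everything. The format of those summaries and the adverse event form are not shown, so it cannot be said that self-harm would go unseen in them.

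What survives is that one criterion is narrowed so as to omit the first-named risk, and that the later paragraphs do not carry forward the commitment to report every serious event promptly.

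**Conclusion.** The point holds in a limited form. On the legible text, self-harm that needs intervention to prevent permanent damage is classed as non-serious when it is not life-threatening and leads to no admission, lasting or significant disability or listed diagnosis. Separately, the three reporting paragraphs give different triggers: a serious but expected event is prompt under one and has no explicit clock under the other two beyond the annual report, unless it is a risk/benefit change or an undefined sponsor-reportable event.

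The number of events affected cannot be estimated, because the documents give no expected rate of self-harm. With 60 participants, one such event could decide whether the pilot reports any serious event. The conclusion assumes that the blank entry does not name self-harm and that the definition is meant to be exhaustive, as its wording says. Neither issue touches the neural-target analysis. Both concern safety classification and reporting, and should be corrected.

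**What to change.** 1. In Section 11.0, change *this is defined as* to *this includes but is not limited to*, restore or delete the blank entry, and name self-harm, and MRI-related injury, that require medical intervention.
2. Replace the reporting sentences in Section 11.0 (Independent Oversight; Requirements for Adverse Event reporting) and Section 12.0 (Unanticipated Problems) with one table of event class by recipient and clock. It should state explicitly how expected serious events and non-serious events are handled, define an unanticipated event and an event requiring report to the sponsor, and agree with IRB and NIMH requirements. Those requirements are not in the documents, so the clocks are left to that reconciliation.

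The cost is amendment wording and an updated adverse event form, with no added visits or staff. The downside is that a few more events may be labelled serious.
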